6.13. Protocol Deviations

Protocol deviations will be identified throughout the study. Important protocol deviations are defined as those deviations from the protocol likely to have a significant impact on the completeness, accuracy, and/or reliability of the study data or that may significantly affect a patient's rights, safety, or well-being.

A separate document known as the “The AMAH Trial Issues Management Plan” describes the categories and subcategories of important protocol deviations and whether or not these deviations are important protocol violations.

The number and percentage of patients having important protocol deviation(s) will be summarized within category and subcategory of deviations by cohort for ITT population.

A by-patient listing of important protocol deviations will be provided.

6.14. Analysis for Japan Addendum

Protocol Addendum I6T-MC-AMAH(1.1) is performed in Japan to enable the inclusion of patients with generalized pustular psoriasis (GPP) and erythrodermic psoriasis (EP) to fulfill the needs for Japan submission. Appendix 1 provides the details of analysis for the Japan Addendum.

6.15. Interim Analyses and Data Monitoring

Data Monitoring Committee (DMC): One DMC, consisting of members external to Lilly, will be established for interim safety monitoring across Studies I6T-MC-AMAK, I6T-MC-AMAJ, I6T-MC-AMAH and I6T-MC-AMBK in patients with psoriasis. This committee will consist of a minimum of 3 members, including a physician with expertise in dermatology and a statistician. No member of the DMC may have contact with study sites. A Statistical Analysis Center (SAC) will prepare and provide unblinded safety data to the DMC. The SAC members may be Lilly employees or from third-party organizations designated by Lilly. However, they will be external to the study team and will have no contact with sites and no privileges to influence any change in the ongoing study. Access to the unblinded safety data will be limited to the DMC and the SAC or their designees. The study team will not have access to the unblinded data. Only the DMC is authorized to evaluate unblinded data. The purpose of the DMC is to advise Lilly regarding continuing patient safety; however, the DMC may request key efficacy data to put safety observations into context and to confirm a reasonable benefit/risk profile for ongoing patients in the study. Study sites will receive information about interim assessments ONLY if they need to know for the safety of their patients. This committee will make recommendations as to whether it is scientifically and ethically appropriate to continue enrollment, discontinue a treatment group, or discontinue the study. Details outlining the roles and responsibilities of the DMC will be finalized in the DMC charter.

Interim Database Lock: An unblinded interim analysis may be performed to support a regulatory submission. Additional yearly or ad-hoc interim analysis may be performed along with the 4-month safety update or to meet any external regulatory needs.

Final Database Lock: A final database lock will occur after the Post-Treatment Follow-Up Period is completed.

6.16. Annual Report Analyses

Based on regulatory requirements for the Development Safety Update Report (DSUR), reports will be produced (if not already available from the study CSR) for the reporting period covered by the DSUR.

6.17. Clinical Trial Registry Analyses

Additional analyses will be performed for the purpose of fulfilling the Clinical Trial Registry (CTR) requirements.

Analyses provided for the CTR requirements include the following:

Summary of AEs, provided as a dataset which will be converted to an XML file. Both SAEs and “Other” AEs are summarized by treatment group, by MedDRA preferred term.

- An AE is considered “Serious,” whether or not it is a TEAE.
- An AE is considered in the “Other” category if it is both a TEAE and is not serious. For each SAE and “Other” AE, for each term and treatment group, the following are provided:
 - the number of participants at risk of an event
 - the number of participants who experienced each event term
 - the number of events experienced.
- Consistent with www.ClinicalTrials.gov requirements, “Other” AEs that occur in fewer than 5% of patients/subjects in every treatment group may not be included if a 5% threshold is chosen (5% is the minimum threshold).
- AE reporting is consistent with other document disclosures for example, the CSR, manuscripts, and so forth.

7. Unblinding Plan

Refer to a separate blinding and unblinding plan.

8. References

- Heitjan F. and Little RJA. (1991), Multiple imputation for the fatal accident reporting system. *Applied Statistics*. 1991;40:13–29.
- PhUSE resouces page. Analyses and Displays Associated with Outliers or Shifts from Normal to Abnormal: Focus on Vital Signs, Electrocardiogram, and Laboratory Analyte Measurements in Phase 2-4 Clinical Trials and Integrated Summary Documents. 2015. Available at http://www.phusewiki.org/docs/CSS%20White%20Papers%202016/CS_WhitePaper_Outliers_Shifts_v1.0.pdf. Accessed September 18, 2017.
- Schenker N. and Taylor JMG. (1996), Partially parametric techniques for multiple imputation. *Computational Statistics and Data Analysis*. 1996;22:425–446.

9. Appendices

[figure not shown]
Appendix 1. Analysis Plan for Japan Addendum

App 1.1. Japan Addendum Design and Objectives

The main protocol for Study AMAH enrolls patients with plaque psoriasis (Cohort 1). AMAH(1.1) addendum will enroll Japanese patients originating from Study AMAJ who are diagnosed as GPP by the Japanese Dermatological Association or EP who have $\geq 80\%$ body surface area (BSA) involvement (with inflammatory erythema). These patients will continue to receive 250 mg mirikizumab every 8 weeks (Q8W) SC for up to a total of 208 weeks (Cohort 2).

Approximately 8 patients with generalized pustular psoriasis (GPP) or erythrodermic psoriasis (EP) will enroll in AMAJ. The number of patients in Cohort 2 will be determined by the number who continue into Study AMAH from Study AMAJ who reside in Japan and have a diagnosis of GPP or EP.

Objectives in the main protocol are not applied to GPP and EP patients. Selected endpoints in the main protocol are applied to GPP and EP patients. Table AMAH.App.1 shows the addendum objectives and endpoints which are added to the study as exploratory objectives:

Abbreviations: AMAF = I6T-MC-AMAF; AMAJ = I6T-MC-AMAJ; AMAK = I6T-MC-AMAK; AMAH = I6T-MC-AMAH; AMBK = I6T-MC-AMBK; LV = last study visit; miri = mirikizumab given as subcutaneous injection (SC); PBO = placebo; PRN=as needed; pts = patients; Q8W =every 8 weeks; SECU = secukinumab; V = visit; W or w = week.

^aPatients will remain blinded to treatment until the last patient completes the last originator study.

^bPatients receiving 125 mg Q8W may be eligible to escalate to 250 mg Q8W

Table AMAH.App.1. Japan Addendum Objectives and Endpoints

Exploratory
 
To assess the efficacy of mirikizumab in patients with GPP.
	
GPP ONLY
 
Time course of response to treatment as measured by the following measures:
 
 • global improvement score • assessment of dermal symptoms for GPP • change from baseline in PASI • change from baseline in DLQI total score

To assess the efficacy of mirikizumab in patients with EP
	
EP ONLY
 
Time course of response to treatment as measured by the following measures:
 
 • global improvement score • change from baseline in PASI • change from baseline in DLQI total score

Abbreviations: DLQI = Dermatology Life Quality Index; EP = erythrodermic psoriasis; GPP = generalized pustular psoriasis; PASI = Psoriasis Area and Severity Index.

App. 1.2. Japan Addendum General Considerations

The benefit/risk profile to support global registrations will be based on the analysis of Cohort 1. Patients enrolled in Cohort 2 will not be included in the analysis supporting global registrations. To support registration in Japan, efficacy and safety analyses for plaque psoriasis, GPP, and EP will be conducted separately.

The Japan Addendum Intent-to-Treat (ITT) Population – Patients with GPP or EP is defined as all GPP and EP patients who enrolled in the Japan addendum, even if the patient does not take the assigned treatment, does not receive the correct treatment, or otherwise does not follow the protocol. All patients are assigned to mirikizumab treatment. Efficacy and safety analyses will be conducted on this population. GPP and EP patients will be reported separately.

The definitions of the baselines for efficacy and safety analyses in the Japan addendum are the same as in the main protocol/SAP.

No formal inferential statistics will be performed. Data will be summarized for GPP and EP patients separately. The methods of summary are the same as in the main SAP.

The following general summaries and/or listings will be provided based on Japan Addendum ITT Population – Patients with GPP or EP:

- Patient disposition including treatment disposition and study disposition
- Patient demographics and other baseline characteristics

- Add baseline GPP dermal symptom total score
- Prior medications and concomitant medications
- Study treatment exposure
- Listing of randomization/treatment assignment
- Important protocol deviations
- Treatment compliance

App. 1.3. Japan Addendum Efficacy/Health Outcomes

Table AMAH.App.2 includes the description and derivation of the additional efficacy measures and endpoints that are collected in the Japan Addendum.

Table AMAH.App.3 provides the detailed analyses for efficacy/health outcomes analyses in the Japan Addendum.

Table AMAH.App.2 Description and Derivation of Additional Efficacy/Health Outcomes Measures and Endpoints for Japan Addendum

Measure	Description	Variable	Derivation/Comment	Imputation Approach if with Missing Components
Global Improvement Score	
 Collected for patients with GPP or EP from Week 2. Assessed in the 4 grades by comparing the psoriatic findings: (1) resolved, (2) improved, (3) unchanged, (4) worsened. Assessed based on the comparison of the psoriatic findings, sPGA, PASI score, and other evaluations with those at the baseline. 	Global improvement score	As collected	Single item, missing if missing.
Assessment of dermal symptoms	
 According to the Japanese Dermatological Association GPP revised criteria.^a Performed only for patients with GPP. Skin symptoms are assessed by the score with the area of erythema (on a 0-3 scale), the area of erythema with pustules (on a 0-3 scale), and the area of skin edema (on a 0-3), where 0 = none; 1 = mild; 2 = moderate; 3 = severe. 	GPP dermal symptom total score	Sum of scores of the area of erythema, the area of erythema with pustules, and the area of skin edema. Range from 0-9.	If any individual score is missing, the total score will not be calculated, hence missing.

Abbreviations: EP = erythrodermic psoriasis; GPP = generalized pustular psoriasis; PASI = Psoriasis Area and Severity Index; sPGA = static Physician's Global Assessment.

^a (Terui et al. [WWW]).

Table AMAH.App.3. Description of Efficacy/Health Outcomes Analyses for Japan Addendum

Measure	Variable	Analysis Method	Population	Time Point and Period
Global Improvement Score	Global improvement score	Descriptive analysis with Observed	Japan Addendum Intent-to-Treat Population – Patients with GPP or EP	All scheduled visits
GPP dermal symptom total score	GPP dermal symptom total score change from baseline	Descriptive analysis with Observed	Japan Addendum Intent-to-Treat Population – Patients with GPP	All scheduled visits
PASI	PASI change from baseline	Descriptive analysis with Observed	Japan Addendum Intent-to-Treat Population – Patients with GPP or EP	All scheduled visits
DLQI	DLQI total score change from baseline	Descriptive analysis with Observed	Japan Addendum Intent-to-Treat Population – Patients with GPP or EP	All scheduled visits

Abbreviations: DLQI = Dermatology Life Quality Index; EP = erythrodermic psoriasis; GPP = generalized pustular psoriasis; PASI = Psoriasis Area and Severity Index.

App. 1.4. Japan Addendum Safety Analyses

The following safety summaries will be provided for the Japan Addendum Intent-to-Treat (ITT) Population – Patients with GPP or EP:

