6.3.1. As Observed Analysis

The “as observed” strategy is used in so-called “observed cases” or “completers” analysis ubiquitous in the literature but is not one of the recommended strategies in the ICH E9(R1). For this analysis, only data from completers at the visit are relevant, and therefore the analysis does not need to deal with missing data. This estimand is based on the subset of patients who would complete treatment through visit T if assigned to it. Therefore, this estimand is conditional and targets the effect of treatment conditional on completion of treatment through the time point of interest. Because the estimand is defined for a subpopulation conditional on an intercurrent

event, it is not causal. Summary based on observed data at each post-baseline visit will be provided.

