6.3.4. Modified Non-responder Imputation

The modified non-responder imputation (mNRI) method will be used to implement the composite strategy [ICH E9(R1)] for handling intercurrent events. This strategy is used to assess the combination of the effect of study treatment with the occurrence of an intercurrent event. For the mNRI method, the patient's response status is defined based on if the patient meets the clinical requirements for response at the predefined time AND the treatment-related contraindication reasons of discontinuation. The outcomes after the discontinuation for treatment-related reasons are considered failure/nonresponse, as in nonresponder imputation (NRI). Discontinuation for reasons that are considered unrelated to study treatment will not be considered a contraindication, thus the resulting outcomes will be imputed by MI. Patients will be considered as non-responders for the mNRI analysis at the analysis time point if they do not meet the clinical response criteria or have missing clinical response data due to discontinuation from study treatment with a reason of adverse event (AE) including death, or lack of efficacy. For patients discontinuing treatment with any other reason, the MI method (Section 6.3.2) will be used. The mNRI method will be the primary analysis method for categorical efficacy and health outcome variables.

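### The Japan addendum summarises the global improvement score by observed cases only; an all-enrolled denominator beside it would be a cheap improvement

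*SAP*

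**What the plan says.** SAP Appendix 1 covers Japanese patients with GPP or EP who roll over from Study AMAJ. App. 1.2 defines their intent-to-treat population as everyone enrolled in the addendum, whatever treatment they took, and places efficacy analyses on it. It gives the purpose as "To support registration in Japan, efficacy and safety analyses for plaque psoriasis, GPP, and EP will be conducted separately". On method it says "The methods of summary are the same as in the main SAP".

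Table AMAH.App.3, introduced as the detailed specification, has four rows: global improvement score, GPP dermal symptom total score, PASI change and DLQI change. Each row names one method, "Descriptive analysis with Observed". Table AMAH.App.2 grades the global improvement score as "1) resolved, (2) improved, (3) unchanged, (4) worsened", takes it as collected, and handles a gap as "Single item, missing if missing".

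Section 6.3.1 explains what observed means: "For this analysis, only data from completers at the visit are relevant, and therefore the analysis does not need to deal with missing data". It calls the resulting estimand conditional on completing treatment and not causal, and says the strategy "is not one of the recommended strategies in the ICH E9(R1").

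For the main study, Section 6.3.4 states: "The mNRI method will be the primary analysis method for categorical efficacy and health outcome variables". That method counts stops for adverse event, death or lack of efficacy as non-response. In Table AMAH.6.4, every binary endpoint has NRI, mNRI and multiple imputation listed beside Observed.

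**The concern.** In the main study, no responder endpoint rests on observed cases alone. In the addendum, the one ordinal response measure does. A patient who worsens and stops contributes to the grade distribution up to the last visit attended and then vanishes from it. The remaining patients' percentages rise without any of them changing.

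Under the main protocol, dropout is unlikely to be unrelated to response. Section 8.2 has a patient who needs another effective psoriasis agent leave the study before that agent starts. Addendum patients are already on 250 mg, and the only dose change described in Section 7.4 is from 125 mg to 250 mg. Treatment failure would therefore tend to end in exit. The addendum protocol is not among the documents and may differ.

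What is at stake is how a reader of the Japanese submission sees the time course of response over up to 208 weeks in two very small groups, where each patient moves the percentage visibly.

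**Working it through.** **Inputs**

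- About 8 GPP and EP patients together are expected in Study AMAJ (SAP App. 1.1). The split is not given.
- Completion of 80–90% and continuation of 80–90% (SAP Section 5.2), stated for the whole study. Check: 205 + 1440 + 500 + 300 = 2445; 2445 × 0.64 = 1565 and 2445 × 0.81 = 1980, in line with the stated 1600 to 2000.
- Dropout and response among addendum patients: not given, so both are varied below.
- Responder grouping: not defined in the SAP. Resolved or improved is used here as an assumption.

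**Patients likely to enter.** Applying the study-wide assumption to 8 patients gives 8 × 0.64 = 5.1 to 8 × 0.81 = 6.5, divided between two disease groups.

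**Effect of the denominator.** Let N be the number enrolled, d the number stopped for adverse event, death or lack of efficacy, and r the number resolved or improved at the visit. No other data are missing.

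- Observed = r/(N − d)
- All enrolled = r/N
- Gap = r·d / [N(N − d)]

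| N | d | r | Observed | All enrolled | Gap (points) |
|---|---|---|---|---|---|
| 8 | 1 | 7 | 100% | 87.5% | 12.5 |
| 8 | 1 | 4 | 57.1% | 50.0% | 7.1 |
| 8 | 1 | 0 | 0% | 0% | 0 |
| 8 | 2 | 6 | 100% | 75.0% | 25.0 |
| 5 | 1 | 4 | 100% | 80.0% | 20.0 |
| 4 | 1 | 3 | 100% | 75.0% | 25.0 |
| 4 | 1 | 2 | 66.7% | 50.0% | 16.7 |
| 4 | 2 | 2 | 100% | 50.0% | 50.0 |

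The gap is never negative. It is zero only when nobody stops for these reasons or nobody remaining has improved. The second row also shows the drift. Suppose 4 of 8 are improved while the failing patient is still attending (50.0%). Once that patient leaves, the same four are 4 of 7 (57.1%).

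**Chance that it matters at all.** If each patient independently had a 20% chance of such a stop (assumption; range 10–30%), the chance of at least one is 1 − 0.8^5 = 67% with 5 patients (41–83%) and 1 − 0.8^8 = 83% with 8 patients (57–94%).

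**Whether other outputs repair it.** App. 1.2 plans treatment and study disposition, and App. 1.4 plans listings and summaries of serious adverse events and of adverse events leading to stopping. Protocol Section 9.2 does not treat lack of drug effect as an adverse event, so a stop for lack of efficacy would show only in disposition. The main Schedule of Activities collects PASI, sPGA and DLQI at early termination, but the SAP gives no rule mapping that visit to a scheduled one. Even with such a rule, the patient would still be absent from later visits.

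**The case against.** The case on the other side is substantial, and most of it limits the point without removing it.

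- **Status.** App. 1.1 makes these endpoints exploratory. App. 1.2 rules out formal inference and keeps these patients out of the analysis supporting global registrations. A reader might infer that a pivotal response rate for Japan is biased. The documents do not support that: the score has four grades, no responder cut-off is defined, and nothing is tested.
- **Contradiction.** A reader might infer that App. 1.2 promised mNRI for this score and the table withdrew it. NRI and mNRI both need a clinical response criterion, and Section 6.3.3 offers NRI for binary variables as something that may be used. Section 6.3.4 does speak of categorical variables, so the text is ambiguous. Observed is itself a main-SAP method. What stands is a general sentence and a specific table that need reconciling.
- **Scope.** All four rows use Observed, but three are score changes, for which the main SAP uses Observed and multiple imputation for comparable measures and never NRI or mNRI. Multiple imputation is not workable here: Section 6.3.2 draws from 5 donors, which a group of about 4 cannot supply. Only the global improvement score needs a further summary.
- **Visibility.** Stops are not concealed, since disposition and adverse-event outputs are planned. They do not, however, correct the by-visit percentages.
- **Plain NRI has its own bias.** Section 5 lets treatment end at commercial availability. Counting every missing value as failure would score administrative endings as treatment failures. This objection stands, and the fix allows for it.

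**Conclusion.** The point holds as a low-cost improvement. As written, Table AMAH.App.3 lets patients who stop for adverse event, death or lack of efficacy leave the denominator of the global improvement score, so the percentage in the better grades can be overstated at later visits. The direction follows from the SAP's definition of the method. The size does not: it depends on dropout and response, which the documents do not give.

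A reader might take 12.5 points as the bias for any one stop among 8 patients. That figure needs all 7 others to improve; it is 7.1 points if 4 of 7 do, and nil if none do. Nor do the documents show that any such stop will occur. The consequence is confined to exploratory, descriptive percentages in about 8 patients at most, and no test or global registration analysis is affected.

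The conclusion assumes a resolved-or-improved grouping and that the addendum protocol, which was not available, does not already settle the display.

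**What to change.** - **Global improvement score.** In Table AMAH.App.3, keep the Observed summary and add a by-visit summary whose denominator is all GPP (or all EP) patients in the Japan Addendum intent-to-treat population. Show the four grades plus two further categories: (a) stopped for adverse event, death or lack of efficacy; (b) missing or stopped for any other reason, including administrative end of study.
- **Derived percentage.** Define the responder grouping, for example resolved or improved. Count category (a) as not improved, and print category (b) separately beside the percentage so that administrative endings are not silently read as failures. Do not use multiple imputation at this size.
- **Dermal symptom score, PASI and DLQI changes.** Keep Observed. Print n/N at each visit, and list each discontinued patient's last value and reason for stopping.
- **Text.** Amend the App. 1.2 sentence on summary methods so that it agrees with the table.

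The cost is one appendix edit, a responder grouping to agree, and a few lines of programming for about 8 patients. The reported percentage will be lower if patients stop for failure.
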